### 2.3.6 All-cause mortality at 30 Days and 12 Months

To understand the impact of COVID-19 pandemic on all-cause mortality, sensitivity analysis will be performed. All analyses will be performed on subjects in the AP.

All-cause Mortality at 30 days will be analyzed as follows:

Number of deaths reported at 30 days post index procedure (i.e.  $0 \leq \text{Number of days since index procedure} \leq 30$ ) will be summarized with subject count and rates; rates will be estimated as proportion of subjects who died within 30-Day post procedure.

[REDACTED]

Kaplan–Meier (KM) method will be used to estimate the mortality rate at 12-months.

[REDACTED]

## 2.4 Sample Size Calculations

[REDACTED]

[REDACTED]

[REDACTED]

## Statistical Analysis Plan

### 2.5 Interim Analysis

No formal interim analysis is planned for this trial. As such, no formal statistical rule for early termination of the trial is defined. Interim study reports with descriptive analysis may be provided for Investigator meetings, Ethics committee review or reimbursement purposes.

### 2.6 Timing of Analysis

Final analysis will be conducted after all enrolled subjects (First generation and Next generation Portico delivery system have either been terminated or completed the 12-month follow-up.

### 2.7 Subgroups for Analysis

Subgroup analyses will be performed to evaluate endpoints across study cohorts (first generation delivery system vs. FlexNav delivery system).

Baseline Characteristics (refer to section 3.1) and study endpoints (refer to section 2.3) will be descriptively summarized for each subgroup; no hypotheses tests will be performed.

Results for both subgroups will be presented within the same output table.

### 2.8 Handling of Missing Data

There is no plan for imputing missing data for this clinical investigation. All analyses will be performed on available data and additional considerations due to the COVID-19 pandemic are detailed where applicable.

## Statistical Analysis Plan

### 2.9 Poolability Analysis

No poolability analysis is planned for this registry.

### 2.10 Multiplicity Adjustments

There are no multiplicity adjustments planned for this registry.

### 2.11 Adjustments for Covariates

Unless otherwise specified, no adjustments for covariates will be made for any of the variables in the analyses.

## 3 ADDITIONAL DATA

All additional data are descriptive and will be summarized as described below.

### 3.1 Baseline, Demographic Characteristics

Baseline and medical characteristics such as age, gender, Euroscore, STS mortality risk score, cardiovascular history, neurovascular history, etc. will be summarized using appropriate summary statistics.

### 3.2 Adverse Events

All adverse events (AEs) reported will be summarized by seriousness (serious AE vs. nonserious AE), primary relationship (device, procedure, and unrelated).

The follow definitions will apply:

- AE: Adverse Events (Non-serious and non-device or procedure related)
- ADE: Adverse Device Effects (Non-serious and device or procedure related)
- SAE: Serious Adverse Events (Serious and non-device or procedure related)
- SADE: Serious Adverse Device Effects (Serious and device or procedure related)

The number of events and number of subjects who experienced one or more incidents of the adverse event category of interest will be presented for each category. Categories will be non-overlapping.

All events adjudicated as related or possibly related to COVID-19 will also be summarized as above.

Evaluation of all-cause Mortality at 30 days is discussed in section 2.3.6

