5.4.3 Pre-discharge Visit

The pre-discharge visit will take place at the time of hospital discharge or within seven days after the index procedure, whichever occurs first. If the patient is expected to be discharged over the weekend, the discharge tests may be completed on the last weekday prior to discharge. The assessment will include:

- Physical assessment
- Blood sample (Creatinine, Hemoglobin, Troponin, if available, as part of standard of care)
- Anti-platelet and anti-coagulation medication assessment
- Adverse events assessment
- Pacemaker dependency assessment (as applicable)
- Data on resource utilization will be collected to determine the costs associated with hospitalization for a Portico implant procedure

5.4.4 30 Day Follow-up Visit

Each patient will return to the participating institution for a follow-up visit at 30 days (30+90 days) post index procedure. The scheduled visit window is calculated from the date of implant procedure.

The following procedures must be completed at the 30-day follow-up visit:

- Physical assessment
- Blood sample (Creatinine, Hemoglobin, troponin) if available as part of standard of care
- Echocardiogram*
- NYHA functional status classification
- Completion of QoL questionnaire (EQ5D-3L)
- Heart rate and rhythm assessment
- Anti-platelet and anti-coagulation medication assessment
- Adverse events assessment
- Pacemaker dependency assessment (as applicable)

Sponsor Representatives may be involved in providing support during the follow-up procedures.

* Each site will be responsible for performing and interpreting the 30-day follow-up echocardiogram using the VARC-2 definitions. Echocardiograms will be sent to an independent Echocardiographic Core Laboratory for further analysis. Exams should be recorded in DICOM format and should be de-identified prior to sending to the sponsor.

5.4.5 12 Months Vital Status/Survival Status

Each patient will have a survival status check at 12 months (-7 days, +45 days) post index procedure. The scheduled visit window is calculated from the date of implant procedure. The vital status check will be performed to determine patient survival at 12 months only and may be conducted via an in-office visit or by telephone call with the patient during the visit window.

Every effort should be made to contact the subject for the 12 month vital status/mortality check. The subject should not be considered 'lost to follow-up' until:

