8.2 Safety Reporting

Safety surveillance within this study and the safety reporting performed both by the Investigator (per local country requirements) and Sponsor commences at the time of procedure.

The safety surveillance and the safety reporting will continue until the final study visit has been performed, the subject is deceased, the subject/Investigator concludes their participation into the clinical investigation or the subject withdraws from the clinical investigation.

All adverse event data will be collected through the 30 day visit and will be reported to the Sponsor through the electronic data capture system (EDC). All deaths will be collected throughout the clinical study and will be reported to the Sponsor through the EDC using the applicable CRF. The Investigator will record all reportable adverse events and deaths on the appropriate case report forms.

Records relating to the subject's subsequent medical course must be maintained and submitted (as applicable) to the Sponsor until the event has subsided or, in case of permanent impairment, until the event stabilizes and the overall clinical outcome has been ascertained. Adverse events will be monitored until they are adequately resolved, the subject is withdrawn, or completes the study. At the 1 year vital status check, only mortality status will be collected.

For the purposes of this clinical investigation, the following events will be reported through the 30 day follow up visit with deaths reported through one year. All adverse events will be reported as soon as possible. Serious Adverse Events will be reported no later than 3 calendar days after becoming aware of the event or as per the investigative site's local requirements, if the requirement is more stringent than those outlined (see Appendix B: Definitions).

1. VARC-2 Adverse Events
 - Death

- Myocardial infarction
 - Vascular access site and access-related complications
 - Stroke/TIA
 - Bleeding events
 - Acute kidney injury
 - Coronary Obstruction
 - Pacemaker
2. All Adverse Device Effects
 3. All Serious Adverse Events (whether or not the event is considered device or procedure related)

Non-serious adverse events documentation and reporting are limited to cardiovascular and neurovascular events only; all events must be reported regardless of their relationship with the device or the procedure.

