8.2.1 Subject Death

Subject deaths will be documented and reported to the Sponsor as soon as possible but no later than 3 calendar days after becoming aware of the event. All deaths should be reported via an Adverse Event, a Withdrawal form and a Product Out of Service form.

Source documentation (including any hospital records, autopsy reports and death certificates) is required and should be provided to the sponsor for Adjudication purposes.

In the event of a subject death, an autopsy should be performed whenever possible and the Portico valve explanted and returned to the Sponsor for evaluation.

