#### 2.3.1 Evaluation of the VARC-2 event rates at 30 days from the index procedure.

For each VARC-2 adverse event reported within 30 days of index procedure (i.e.  $0 \leq$  Number of days since index procedure  $\leq 30$ ), number of events, number of subjects with event and event rate will be provided.

Evaluation of all-cause Mortality is discussed in section 2.3.6.

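### The adverse event table in SAP 3.2 has no time window, so its serious event counts mix non-fatal events followed to day 30–120 with deaths followed to 12 months

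*SAP*

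**What the plan says.** SAP 3.2, placed under additional data, states that "All adverse events (AEs) reported will be summarized by seriousness" and by relationship to device or procedure. There are four non-overlapping categories: AE, ADE, SAE and SADE. Here SAE means serious and unrelated to device or procedure; a related serious event is an SADE. For each category, "The number of events and number of subjects who experienced one or more incidents of the adverse event category of interest will be presented". No limit by day, visit or person-time is given. The only pointer about time is a cross-reference to SAP 2.3.6 for 30-day mortality.

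The endpoint sections do set limits. SAP 2.3.1 begins "For each VARC-2 adverse event reported within 30 days of index procedure" and spells this out as day 0 to day 30. SAP 2.3.6 uses the same window for 30-day mortality and Kaplan-Meier for 12 months.

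The protocol sets the collection periods:

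- Protocol 8.2: "All adverse event data will be collected through the 30 day visit", and later in the same section, "the following events will be reported through the 30 day follow up visit with deaths reported through one year". It adds that the one-year check records mortality only.
- Protocol 5.4.4 and Table 4: the subject returns for a "follow-up visit at 30 days (30+90 days) post index procedure", shown in the table as day 30 to 120.
- Protocol 8.2.1: "All deaths should be reported via an Adverse Event, a Withdrawal form and a Product Out of Service form".
- Protocol Appendix B: death is the first criterion for a serious adverse event.

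**The concern.** A count of subjects with an event can be read only against a known period of observation. Here the end of that period depends on when a subject happened to attend the 30-day visit and on whether the event was fatal. Two subjects who both comply with the protocol can be observed for 30 and for 120 days. After that visit, deaths are the only serious events still collected, and they go on the form that feeds the table.

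The registry's objective is to characterise procedural safety, and the table will stand beside VARC-2 rates that are true 30-day figures. Readers are likely to take the serious event counts as 30-day figures too, or as 12-month figures because they include deaths to 12 months. They are neither. SAP 3.2 also summarises COVID-19-related events in the same way, so that summary has the same problem.

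**Working it through.** **1. Reproduce the windows.** From Protocol 5.4.4, the 30-day visit falls on day 30 + 0 = 30 to day 30 + 90 = 120. From Protocol 5.4.5, the 12-month check falls on day 365 − 7 = 358 to day 365 + 45 = 410. Both match Table 4.

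**2. Compare the observation periods.**

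| Type of event | Collected until | Enters the SAP 3.2 count? |
|---|---|---|
| Non-fatal, before the 30-day visit | day 30 to 120, by subject | yes |
| Non-fatal serious, month 9 | not collected | no |
| Death, month 9 | 12-month check, on an Adverse Event form | yes, as SAE or SADE |

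- Non-fatal period between compliant subjects: 120/30 = 4-fold.
- Fatal against non-fatal period: 365/120 = 3.0 to 365/30 = 12.2 times, and up to 410/30 = 13.7 times at the end of the 12-month window.

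These are nominal periods for subjects seen within the window; death, withdrawal or a late visit changes them. Failed implants have their own rule in Protocol 5.4.2: 30 days of adverse event collection, then withdrawal.

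**3. Late deaths, per 1000 subjects.** Inputs: 30-day mortality P30 of 1.6% to 8.5% (Protocol section 2, registries of other valves) and 12-month mortality P12 of 10% to 20% (assumed; not in the documents).

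- Deaths after day 30 = 1000 × (P12 − P30). Lowest: 1000 × (0.10 − 0.085) = 15. Highest: 1000 × (0.20 − 0.016) = 184.
- Deaths after day 120, with a constant hazard from day 30 to day 365: h = −ln[(1 − P12)/(1 − P30)]/335, and deaths by day 120 = 1000 × [1 − (1 − P30) × exp(−90h)]. Lowest: 100 − 89 = 11. Highest: 200 − 69 = 131.

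The second figure counts deaths at a time when no compliant subject is still giving non-fatal data. The event count rises by the full number of late deaths. The subject count rises by less, because some of these subjects already have an event in the same category.

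**4. Visit timing, non-fatal serious events.** Assume a share P30 with a serious event by day 30 and a hazard h per day after that. The share recorded for a visit on day T is 1 − (1 − P30) × exp[−h(T − 30)].

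| Assumed P30 | Visit on day 30 | Visit on day 120, h = 0.0005 | Visit on day 120, h = 0.002 |
|---|---|---|---|
| 15% | 15.0% | 18.7% | 29.0% |
| 25% | 25.0% | 28.3% | 37.4% |

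These compare the two ends of the window. For a smaller shift, with P30 = 15%, moving the visit from day 45 to day 75 changes the share from 15.6% to 16.9% (h = 0.0005) or from 17.5% to 22.3% (h = 0.002). That is 1.3 to 4.8 points with no difference in true risk.

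**5. Look for a correcting rule.** The cross-reference in SAP 3.2 concerns 30-day mortality only. It neither removes later deaths from the table nor cuts the table at day 30. SAP 2.8 on missing data and SAP 2.11 on covariates do not address the period. SAP 2.1 and parts of 2.3.6 are blacked out, but SAP 3.2 shows no redaction.

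**The case against.** The best defence is that this is a supplementary table whose proper job is to account for every event reported, and that nothing important depends on it. Much of that is right. VARC-2 rates and 30-day mortality have a fixed day 0 to 30 window, 12-month mortality uses Kaplan-Meier, and no hypothesis is tested. The non-fatal part can be read sensibly as covering the time up to the 30-day visit, so it would be too strong to say that the table cannot be interpreted at all.

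The defence also rules out several stronger readings that a reader might infer:

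- *A false safety difference between delivery systems is built into the plan.* SAP 2.7 requires cohort columns for baseline characteristics (3.1) and endpoints (2.3); it does not name 3.2. The documents also do not say that the second cohort's visits will be later. Sensitivity to visit timing matters only if the sponsor chooses to show the table by cohort.
- *The plan will publish misleading percentages.* SAP 3.2 promises counts. A percentage could come in only through the general rule for categorical data in SAP 2.2.2.
- *Pre-procedure events will be counted.* Table 4 schedules an adverse event assessment at baseline, but Protocol 8.2 says that surveillance and reporting by the investigator and "Sponsor commences at the time of procedure". This is an ambiguity to settle, not a third collection period.
- *Every death after day 30 falls outside non-fatal collection.* For a subject seen on day 120, non-fatal events are collected until then, so only deaths after that visit are unmatched.

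One could also argue that Protocol 8.2 continues safety reporting to the final study visit, which would put fatal and non-fatal events on the same footing. But that section twice ends adverse event collection at the 30-day visit and limits the one-year check to mortality.

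The defence does not explain why serious events with different observation periods should share one unlabelled count.

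**Conclusion.** The point holds for the supplementary adverse event table and no further. As written, SAP 3.2 yields SAE and SADE counts with no single time frame, and no other visible section corrects this. Unrelated late deaths fall in the SAE row; any judged related fall in the SADE row.

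That the periods differ follows from the documents alone. The size does not. The 15 to 184 deaths after day 30 per 1000 subjects, and the 11 to 131 after day 120, rest on an assumed 12-month mortality of 10% to 20% and on 30-day rates from other devices. The day-120 figures also assume a constant hazard. The visit-timing figures rest entirely on assumed risks. This is a low-cost improvement to a secondary output, not a threat to the registry's endpoints.

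**What to change.** Amend SAP 3.2 as follows:

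- Restrict the main AE, ADE, SAE and SADE counts to events with onset on day 0 to 30, the window in SAP 2.3.1. Use the onset date, not the date of report. This window ends no later than scheduled collection for any subject, including failed implants.
- Show events with onset from day 31 to the 30-day visit in a separate table, stating that the length of observation varies by subject.
- Report deaths after day 30 separately, with the 12-month mortality analysis.
- List any event with onset before the index procedure separately.
- Apply the same split to the COVID-19-related summary, and to any display by cohort if one is produced.

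The sponsor should also reconcile the two statements in Protocol 8.2 on when safety reporting ends.

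The cost is a few lines of SAP text and one filter on onset date. No new data are needed and no event is lost. The downside is smaller headline counts and one more table.

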### 3.3 Subject Early Termination

Reasons for early termination including deaths, withdrawals, lost to follow-up, unsuccessful implant, etc. will be summarized.

## Statistical Analysis Plan

### 3.4 Protocol Deviation

Protocol deviations will be summarized by follow-up visit and by deviation category (Inclusion/Exclusion criteria not met, Informed consent, visit not done etc.) using number of events.

### 3.5 30-Day Follow-up

For the purpose of the valve hemodynamic performance evaluation, all echocardiographic data submitted for the 30-day time point will be used for analysis.

## 4 DOCUMENTATION AND OTHER CONSIDERATIONS

All analyses will be performed using SAS® for Windows, version 9.3 or higher.

## 5 ACRONYMS AND ABBREVIATIONS

Acronym or Abbreviation	Complete Phrase or Definition
AE	Adverse Event
AP	Attempted Procedure
CEC	Clinical Events Committee
CIP	Clinical Investigation Plan
CRF	Case Report Form
IP	Implanted Population
KM	Kaplan-Meier
NYHA	New York Heart Association
SAP	Statistical Analysis Plan
SD	Standard Deviation
